## **10.7 Subgroup analyses**

Subgroup analyses will be performed for the primary outcome variable using logistic regression models with test of treatment-subgroup interaction for each of the predefined subgroup variables. The results will be presented as the odds ratio with 95 % confidence interval for each subgroup and the corresponding p-value for interaction between treatment and each subgroup variable.

Subgroups will be analyzed according to the following pre-defined variables:

- Gender
- Age
- Cause of OHCA
- Initial rhythm
- Place of cardiac arrest
- Time to start of CPR
- Time to arrival of EMS
- Neurological severity classification (CPC)

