### 4.2 Secondary objectives

To evaluate whether there is a difference between CO-CPR and S-CPR in survival to hospital admission, neurological favorable survival, defined as survival with cerebral performance category (CPC) 1-2, neurologically intact survival defined as CPC 1 and long-term survival, defined as survival to one year. To evaluate whether there is a difference between CO-CPR and S-CPR in VT/VF as first rhythm and Return of Spontaneous Circulation (ROSC). To compare 30-day survival between CO-CPR and S-CPR in pre specified subgroups.

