#### **6.4.3 Exploratory outcomes:**

- VT/VF as first rhythm
- Return of spontaneous circulation (ROSC)
- Repeated analysis of primary endpoint and all secondary endpoints at 24 months

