### **9.3 Potential benefits**

Survival after OHCA is very poor, in Sweden ranging between 10-12%. Experimental studies and previous randomized trials have shown that successful CPR can be achieved with CO-CPR. Rescue breaths are technically difficult and take time from chest compressions. In non-cardiac causes of OHCA, rescue breathing might be more important. These cases are therefore excluded prior to randomization. CO-CPR could lead to an earlier start of CPR, no interruptions in chest-compressions and could therefore be beneficial for a majority of cases. In cases of OHCA immediate, effective chest compressions is of absolute necessity to increase the otherwise low chance of survival.

Today, Sweden has amongst the highest rates of bystander CPR in Europe making a study like this possible for the first time. An additional simplification of the CPR-algorithm introducing CO-CPR could perhaps increase survival rates in Sweden but has the potential to dramatically increase bystander rates throughout Europe and more.

A simplified method of CPR with shorter CO-CPR courses optimally provided by the Swedish CPR council will be more cost-effective in companies, schools and throughout society and could enhance the care for this patient group nationally and internationally. In summary, whether CO-CPR leads to a survival rate no worse than, equally effective, or even superior to standard CPR in situations where the bystander has previous CPR training remains unclear. This clinical question remains unanswered while millions of people are trained in CPR worldwide each year. The potential benefits of this study are two-fold in the sense that the results can lead to increased survival rates: 1) simplified CPR might be better than traditional CPR b) simplified CPR could lead to more people performing it.

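### Section 10.7 tests treatment-by-subgroup interaction on initial rhythm and time to start of CPR, both of which can be determined after randomisation, so those subgroup odds ratios may be biased if allocation shifts either variable

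*Combined protocol and SAP*

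**What the plan says.** Section 10.7 sets the method: "Subgroup analyses will be performed for the primary outcome variable using logistic regression models with test of treatment-subgroup interaction". Each listed variable gets an odds ratio with a 95% confidence interval per subgroup and an interaction p-value. The list contains, in sequence, "Initial rhythm - Place of cardiac arrest - Time to start of CPR", and it ends with CPC. It is not restricted to values known before randomisation, and no caution is attached to variables recorded later.

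Elsewhere the same quantities have another role:

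- **Rhythm.** Section 4.2 undertakes "To evaluate whether there is a difference between CO-CPR and S-CPR in VT/VF as first rhythm", and section 6.4.3 lists "VT/VF as first rhythm" as an exploratory outcome. Section 8 takes first recorded rhythm from the Swedish Cardiac Arrest Register entry for EMS-treated arrests. No rhythm recorded before randomisation is described.
- **Time to CPR.** Section 9.3 states "CO-CPR could lead to an earlier start of CPR, no interruptions in chest-compressions". Under section 6.2.1 the arm-specific instructions appear after randomisation, but a call with CPR already in progress may also be screened and included.
- **CPC.** Section 6.4.2 makes CPC 1-2 at discharge a secondary outcome.

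**The concern.** A subgroup odds ratio can be read as a treatment effect only if membership of the subgroup does not depend on treatment. Randomisation guarantees this for characteristics fixed beforehand, but not for a measurement taken after the allocated instructions have been given. If CO-CPR changes which patients are found in VT/VF, the shockable stratum contains a different mix of patients in the two arms. The odds ratio inside it then blends any treatment effect with that difference in mix. The same reasoning applies to early and late CPR, for callers who had not begun before randomisation.

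Section 4.2 makes comparison of 30-day survival in prespecified subgroups part of the secondary objectives, so these results will be reported. At stake is a rhythm table that could suggest harm where there is none, or show no effect in either stratum when a benefit acts by preserving a shockable rhythm.

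**Working it through.** The plan gives no figure on this point to reproduce, and no rhythm distribution or stratum-specific survival. All inputs below are assumptions, except the 1630 per group in section 10.5.

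**1. Order of events.** Randomisation, then instructions (6.2.1); the intervention ends when EMS or first responders arrive (6.2.2); first rhythm comes from the register record of the EMS-treated arrest (8). Rhythm is therefore recorded after allocation has had the chance to act. Time to CPR is fixed before allocation only where CPR was already under way.

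**2. Rhythm, no effect on anyone's survival.** Assume 30% shockable under S-CPR, with survival of 28% if shockable and 4% if not: overall 0.30 × 0.28 + 0.70 × 0.04 = 11.2%. Let CO-CPR move a share d of patients into the shockable stratum, each keeping 4% survival. Then

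shockable survival under CO-CPR = (0.30 × 0.28 + d × 0.04) / (0.30 + d).

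| d | Shockable survival, CO-CPR v S-CPR | Stratum OR (truth 1.00) |
|---|---|---|
| 0 | 28.0% v 28.0% | 1.00 |
| 0.02 | 26.5% v 28.0% | 0.927 |
| 0.03 | 25.8% v 28.0% | 0.895 |
| 0.05 | 24.6% v 28.0% | 0.838 |

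Overall survival stays at 11.2% in both arms throughout.

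**3. Rhythm, full benefit to those moved.** With d = 0.03 and moved patients surviving at 28%, CO-CPR survival is 0.33 × 0.28 + 0.67 × 0.04 = 11.92%, against 11.2%. Both stratum odds ratios are 1.00.

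**4. Sensitivity to who moves.** Take 25% to 35% shockable, survival of 25% and 4% in patients whose rhythm is the same under either arm, moved patients surviving at 4% to 25%, and no effect of allocation on survival. A 2-point shift gives a shockable OR of 0.92 to 1.00 and a non-shockable OR of 0.86 to 1.00. A 5-point shift gives 0.82 to 1.00 and 0.70 to 1.00, with the ratio of the two between 0.82 and 1.43. The interaction can be displaced in either direction.

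**5. Time to CPR.** Assume 50% early under S-CPR, survival of 15% (early under either arm) and 7% (late under either arm), moved patients at 7% to 15%, and no survival effect. With 10 points moved at 7% survival, the early stratum under CO-CPR is (0.50 × 0.15 + 0.10 × 0.07) / 0.60 = 13.7% against 15%, an OR of 0.90. With 10 points moved at 15%, the late stratum is 7% against (0.10 × 0.15 + 0.40 × 0.07) / 0.50 = 8.6%, an OR of 0.80. Five points give 0.94 to 1.00 (early) and 0.89 to 1.00 (late). No shift gives 1.00.

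**6. Size against sampling error.** With 1630 per arm and d = 0.03 as in step 2, the shockable strata hold 0.33 × 1630 ≈ 538 and 0.30 × 1630 = 489 patients. The standard error of the log OR, from the square root of the summed reciprocals of the four expected cell counts, is about 0.141. Since ln(0.895) = −0.111, the displacement is about 0.8 standard errors, with an expected 95% interval of about 0.68 to 1.18. For the interaction (standard error about 0.258) it is about 0.4 standard errors, and about 0.7 with a 5-point shift.

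**The case against.** The best defence has four parts.

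*No shift is shown.* A reader might infer that these odds ratios are biased, or that the protocol expects allocation to change them. The documents support neither reading. Naming VT/VF as an outcome asks a question; it does not assert an effect. Section 9.3 says only that CO-CPR could lead to earlier CPR. With no shift the bias is zero. This stands, and it is why the point is about risk of bias.

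*Time to CPR is the weaker case.* In section 6.2.1 both sets of instructions begin with chest compressions, any delay from randomisation falls on both arms, and CPR already in progress started before allocation. This stands too. What remains is that section 10.7 neither defines the variable nor limits it to calls where it was fixed beforehand.

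*The effect is modest.* The illustrated 3-point displacement lies within sampling error. In step 3 the benefit would still appear in the overall comparison, and its route in the planned comparison of VT/VF by arm. This is fair, but a larger sample would narrow the interval without removing the displacement.

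*Section 10.7 promises no more than an interaction test.* It does not call the variables baseline characteristics. That is true, but an interaction p-value is ordinarily read as evidence of effect modification, and nothing in the section warns against that reading here.

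A reader might also turn to section 9.3 on rescue breaths to argue that rhythm is the decisive subgroup. That passage concerns non-cardiac causes, which correspond to the separate subgroup for cause of arrest.

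**Conclusion.** The concern holds as a conditional one. Initial rhythm is both an outcome compared between arms and a subgroup variable, and time to start of CPR can follow allocation. If allocation shifts either variable, the corresponding odds ratios and interaction p-values may be biased, in a direction that depends on which patients move. On the assumed inputs, a 2- to 5-point rhythm shift with no survival effect gives a shockable-stratum OR of 0.93 to 0.84 instead of 1.00. The documents supply neither the inputs nor evidence of a shift. The case is stronger for rhythm than for time to CPR. CPC, in the same list, is the clearest instance because it is an outcome assessed at discharge. The primary non-inferiority test does not use these variables and is unaffected.

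**What to change.** In section 10.7:

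1. Limit the interaction tests to variables fixed before randomisation.
2. Move initial rhythm, time to start of CPR and CPC to descriptive reporting by arm.
3. Give rhythm-specific results as joint outcomes over all analysed patients in each arm: survival with first rhythm VT/VF, and survival with a non-shockable rhythm. In step 2 with d = 0.03 these would be 8.52% v 8.40% and 2.68% v 2.80%, which sum to 11.20% in both arms. In step 3 they would be 9.24% v 8.40% and 2.68% v 2.80%, so the gain stays visible.
4. If a rhythm-stratified odds ratio is kept for comparability with other studies, label it post-randomisation and not evidence of effect modification.
5. Replace time to CPR with a split by CPR ongoing before randomisation only if the dispatch record or the blinded call audit captures it. Section 6.2.1 has the operator mark prior training or ongoing CPR, but the documents do not show a separate field for ongoing CPR.

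The cost is SAP wording and a small change to the tables; no new data are needed unless the split in item 5 is adopted. The downside is that the customary rhythm-stratified odds ratio loses its standing as a prespecified test of effect modification. Because the trial is under way and the monitoring committee has already reviewed 30-day survival (section 11), the change and its reason should be documented while the researchers remain blinded (section 6.3).

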### **Exclusion criteria:**

- Age 18 or younger
- Collapse is not witnessed
- Bystander has never been taught CPR. (*These bystanders should be instructed to administer CO-CPR in accordance to guidelines*)
- Obvious asphyxia, *i.e.* drowning, strangulation, hanging
- Obvious intoxication or drug overdose
- Pregnancy
- Trauma

**Primary outcome:** 30-day survival

**Secondary outcomes:** Survival to hospital admission, 1-year survival, survival with good neurologic outcome at discharge, defined as cerebral performance category (CPC) 1-2, survival with complete neurologically outcome defined as CPC 1

[figure not shown]

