#### **6.2.4. Phase 5: Follow-up of survival and neurological function**

Survival is evaluated for primary endpoint at day 30 through the Swedish cardiac arrest register (SCAR) through linkage with the Swedish public population register (folkbokföringsregistret). For the secondary outcome of neurologically favorable outcome CPC is obtained through SCAR. In a subset of patients (survivors treated at specifically named hospitals), a comprehensive neurological assessment using Patient Reported Outcome Measurement (PROM) related follow-up is performed between 30-90 days. This follow-up is performed by a nurse and/or behavioral therapists blinded to the intervention allocation. This comprehensive follow up will not be possible in all sites of the TANGO2 trial.

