#### **6.4.2 Secondary outcomes:**

- Survival to hospital admission
- 1-year survival
- Survival with good neurologic outcome at discharge, defined as cerebral performance category (CPC) 1-2
- Survival with complete neurologically outcome defined as CPC 1

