### From the Swedish Cardiac Arrest Register the following variables will be collected:

All EMS units participating in TANGO2 report to the SCAR. For all EMS treated OHCA the following variables will be collected from the Swedish Cardiac Arrest Register:

Date of OHCA, Age, Sex, Location of OHCA, CPR prior to EMS arrival, highest medical educational level of CPR provider, first recorded rhythm, defibrillation, airway management and drug administration, Return of spontaneous circulation (ROSC) and survival to admission to hospital.

In calls where there is no matching report in SCAR, ambulance records will be reviewed; if EMS has performed CPR or the patient had been defibrillated by an AED the case will be classified as "EMS treated" and corresponding variables will be extracted from ambulance records instead.

The EMS will obtain information on what type of CPR that was provided to the patient before their arrival at the scene. This information is obtained by observing on-going CPR at their arrival and asking bystanders what type of CPR they provided. EMS crew will also ask bystanders what kind of CPR training they have according to a three-leveled division of the bystander's medical educational level (a – off-duty professional caregiver, doctor, nurse; b – CPR-trained layman (including off-duty police and fire-fighters); or c – layman with no CPR training). This information is a part of SCAR, but there will be emphasis on obtaining this specific data in the TANGO2 trial. Survival is collected for primary endpoint at day 30 from SCAR through linkage with the Swedish public population register (folkbokföringsregistret). For the secondary outcome of neurologically favorable outcome CPC is obtained through SCAR. In a subset of patients (survivors treated at specifically named hospitals), a comprehensive neurological assessment using Patient Reported Outcome Measurement (PROM) related follow-up is performed between 30-90 days. This follow-up is performed by a nurse and/or behavioral therapists blinded to the intervention allocation. This comprehensive follow up will not be possible in all sites of the TANGO2 trial.

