## 10.5 Power and sample size estimation

We estimated that 3260 patients (1630 in each group) would be needed in the primary analysis PP1 to have 80% power to show that CO-CPR is non-inferior to standard CPR. This calculation is based on the assumptions that the true survival rates after 30 days (primary outcome) in the population for standard CPR is 11% compared with 13.1% for CO-CPR, and that alpha (1 tailed) is set at 2.5%.

We defined 1.0 percentage point or less as the largest difference in survival that is clinically acceptable (i.e. the non-inferiority level which imply that a difference bigger than this would matter in practise). This difference is equivalent to an NNT of 100 (one person of 100 will die among those recommended CO-CPR, due to this recommendation). The reason for accepting this difference relies on the assumption that CO-CPR is easier to teach and perform, and therefore the treatment can be offered to more victims (please see also section 9.3).

In addition, we assumed that 20% will not receive the allocated intervention (e.g. randomized to CO-CPR but received S-CPR instructions or vice versa). We also assumed that 40% of the included patients will be excluded because of exclusion criteria's not possible to detect at the randomization (not OHCA, see section 5.3). Therefore, the recruitment goal was set to 6792 ( $3260 / (0.8 * 0.6)$ ) randomized cases of suspected out-of-hospital cardiac arrest in order to receive 3260 in the primary PP1 analysis. (Please see also Consort Flow Diagram below)

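### Section 10.7 makes CPC, which the plan describes only as a post-arrest outcome, a subgroup variable for 30-day survival, so those results cannot be read as subgroup treatment effects

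*Combined protocol and SAP*

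**What the plan says.** Section 10.7 plans logistic regression of the primary outcome, 30-day survival, with a treatment-by-subgroup interaction for each of eight predefined variables. The reported results are "the odds ratio with 95 % confidence interval for each subgroup and the corresponding p-value for interaction between treatment and each subgroup variable". The eighth variable is "Neurological severity classification (CPC").

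Apart from the abbreviation list, CPC appears elsewhere only as an outcome:

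- Section 1 (Summary), secondary outcomes: "survival with good neurologic outcome at discharge, defined as cerebral performance category (CPC) 1-2".
- Section 4.2: "neurological favorable survival, defined as survival with cerebral performance category (CPC) 1-2, neurologically intact survival defined as CPC 1".
- Section 6.4.2 repeats the CPC 1-2 outcome at discharge and adds "Survival with complete neurologically outcome defined as CPC 1".
- Section 6.2.4, repeated in section 8: "For the secondary outcome of neurologically favorable outcome CPC is obtained through SCAR".

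The register variables in section 8 begin with "Date of OHCA, Age, Sex, Location of OHCA, CPR prior to EMS arrival, highest medical educational level of CPR provider" and go on to rhythm, treatment, ROSC and admission. No neurological status before the arrest is among them. Randomisation takes place during the emergency call (sections 6.2.1 and 10.4).

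**The concern.** A subgroup variable should be fixed before allocation, or at least be beyond its reach. The only CPC that these documents describe is scored after the arrest, so the allocated instruction can affect it. The good categories are also defined as forms of survival. Splitting a survival analysis by such a variable amounts to splitting it largely by its own outcome.

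The documents do not say how CPC is coded in patients who die, so the strata are not defined. A result that is pre-specified and printed with a confidence interval and an interaction p-value carries authority. Here it could suggest that CO-CPR harms or helps some patients when survival is the same in both arms, or it could hide a real effect. The subgroup comparisons are secondary or exploratory (sections 4.2 and 7.1.2), so the primary non-inferiority test is not at stake.

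**Working it through.** The plan gives no figure to reproduce on this point. The argument is structural, and the arithmetic shows how the analysis would behave.

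**Inputs from section 10.5.** 1630 patients per arm; assumed survival: "standard CPR is 11% compared with 13.1% for CO-CPR".

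**Assumptions, not in the documents.** The share g of 30-day survivors with CPC 1-2 in each arm, and the share d of CPC 1-2 patients who die between discharge and day 30.

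**Scale.** Expected survivors are 1630 × 0.11 = 179.3 and 1630 × 0.131 = 213.5. The total is 392.8 of 3260, or about 12%. The number with a discharge CPC is not given; 12% stands in for it.

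**Coding A: deaths form their own category.** That stratum has essentially no 30-day survivors, so its odds ratio cannot be estimated.

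**Coding B: only patients with a score are analysed.** Roughly 12% remain. If no CPC 1-2 patient dies before day 30, survival in that stratum is 100% in both arms and the odds ratio cannot be estimated. Otherwise it rests on 179.3 × g × d/(1−d) deaths per arm. At 11% survival and g = 85%, that is about 1.5, 3 and 8 deaths for d = 1%, 2% and 5%.

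**Coding C: CPC 1-2 against all others, deaths included.** Take 11% survival in both arms, so the true overall odds ratio is 1.00.

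- Survivors among all others: 179.3 × (1 − g).
- Deaths per arm: 1630 − 179.3 = 1450.7, all placed in this stratum for the calculation (the few CPC 1-2 deaths are ignored).
- Odds ratio, CO-CPR over S-CPR: the ratio of the two survivor counts, because the deaths cancel.
- SE of the log odds ratio: the square root of the summed reciprocals of the four counts.

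For 80% against 90%, survivors are 35.9 (S-CPR) and 17.9 (CO-CPR). The odds ratio is 17.9/35.9 = 0.50, the SE is 0.292, and the interval is 0.50 × exp(±1.96 × 0.292) = 0.28 to 0.89.

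| CPC 1-2 among survivors, S-CPR vs CO-CPR | Survivors among all others | Odds ratio (95% CI) |
|---|---|---|
| 85% vs 85% | 26.9 vs 26.9 | 1.00 (0.58-1.72) |
| 82.5% vs 87.5% | 31.4 vs 22.4 | 0.71 (0.41-1.23) |
| 87.5% vs 82.5% | 22.4 vs 31.4 | 1.40 (0.81-2.42) |
| 80% vs 90% | 35.9 vs 17.9 | 0.50 (0.28-0.89) |
| 90% vs 80% | 17.9 vs 35.9 | 2.00 (1.13-3.54) |

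In simulation (20,000 trials per case, Wald test at 5%) this odds ratio is significant in about 5%, 22% and 67% of trials for mix gaps of 0, 5 and 10 points. The overall odds ratio stays near 5% throughout.

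At the planned rates with equal mix, the odds ratio among all others is [0.131(1−g)/0.869] / [0.11(1−g)/0.89] = 1.22 for any g below 1. This is the overall odds ratio again, so the stratum adds nothing.

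**Interaction test under coding C** (40,000 trials per case, 11% survival in both arms, d equal in both arms):

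| d | Not computable (80% vs 90%) | Rejects, equal mix | Rejects, 5-point gap | Rejects, 10-point gap |
|---|---|---|---|---|
| 1% | 38% | 0.1% | 0.4% | 2% |
| 2% | 9% | 1.0% | 2.6% | 9% |
| 5% | 0.1% | 4.0% | 8% | 21% |

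Rejection rates are shares of all simulated trials. The non-computable ones count as not rejecting.

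**The opposite failure.** In a separate simulation of 4 million patients, treatment shifted the CPC-and-death distribution and had no further effect on survival given CPC. The assumed control arm had 12% alive at discharge: 10.5% at CPC 1-2 and 1.5% at CPC 3-4. An overall effect of 11.3% against 13.1% (odds ratio 1.19) became 0.97 within CPC 1-2 and 0.96 within CPC 3-4, with Monte Carlo SE about 0.02. A real benefit vanishes because it acts through CPC.

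**The case against.** The best defence is that a pre-arrest CPC was meant. The label in section 10.7 differs from the outcome wording. The register list in section 8 is also not a complete list of subgroup variables: cause of arrest and time to start of CPR are absent from it too, and section 8 draws on ambulance records, call audits and hospital records as well. So the absence of a baseline CPC from that list is weak evidence on its own. This stands, and the fix allows for it. But no section defines a pre-arrest CPC or says that one is collected, and a reader following the text would use the CPC it describes.

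A second objection is that the larger numbers come from a 10-point mix gap with no basis in the documents. That is fair. At 5 points the intervals include 1. The interaction test rejects no more often than its nominal 5% when the mix is equal, and at most about 8% of the time with a 5-point gap. The case does not rest on false-positive rates, since the result lacks a subgroup meaning even where the error rate is nominal.

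Third, cut-points are also missing for age and the time intervals, and initial rhythm and time to start of CPR may be affected by allocation too. Both points are true. CPC is the clearest case because its good categories contain survival by definition.

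**Conclusion.** The concern holds. As written, section 10.7 stratifies 30-day survival by a post-randomisation variable that largely encodes it. Depending on how deaths are coded, the stratum odds ratios cannot be estimated, rest on a handful of deaths, or restate the overall effect distorted by any difference in survivors' CPC mix. With identical survival, the stratum odds ratio can run from 0.50 to 2.00 over the mixes examined. That range depends on the assumed mixes and on the split of CPC 1-2 against all others; the structural fault depends on neither. The damage is confined to one of eight subgroup analyses. The correction should be made, ideally before unblinding, but the sample size and the primary conclusion do not depend on it.

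**What to change.** Delete the CPC item from the list in section 10.7, leaving seven subgroup variables. Keep CPC 1-2 and CPC 1 as the secondary outcomes in section 6.4.2, compared between arms in all analysed patients. If a pre-arrest CPC was intended and is collected, label it as pre-arrest CPC in section 10.7 and state its source and categories. This point asks for no change to the other seven variables.

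The cost is one list item in the SAP. Data collection, sample size and the primary analysis stay as they are. Readers lose one subgroup result that could not have been interpreted, and they still see CPC by arm.
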